2.2.9 Analysis of Safety Data

New Adverse Events (AEs) will be collected for only 30 days post-randomization (OMT arm) or 30 days post-implantation (ICD arm); these events will be followed throughout the study until study close or AE resolution, but new AEs will not be collected after this period. All reportable non-serious and serious adverse events will be coded by one or more AE specialist. The total number of AE/SAE, and total number of participants experiencing an event will be summarized by treatment. The proportion of participants experiencing an AE/SAE will be calculated for each treatment group. A chi-square test for the difference in the proportion of SAEs will be used to compare treatment groups over all at the 0.05 level. Treatment comparisons will be made for the number of participants experiencing SAE, the number of treatment-related SAE, and for the number of non-serious adverse events.

In addition, the adverse events will be summarized according to the Medical dictionary for Regulatory Activities (MedDRA)³⁷, in terms of system organ class and preferred terms, by treatment and as overall (Tables 17 and 20).

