determined to be the most practical measure of disease burden as a complement to age. The Charlson score will be calculated upon study entry, and will be used as a stratification criterion, but will not be used explicitly as part of the eligibility criteria: entry to the study is based strictly on candidacy as determined through the CMS guidelines for implantation, which doesn't exclude an exclusion for co-morbidity but does list survivability beyond 1 year as a criterion. In addition, the general function level of participants will be measured at baseline using a six-minute walk test for exploratory analysis but not as an eligibility criterion. Therefore, to maximize the simplicity, generalizability and impact of the study, CSP #592 will select patients based solely on their age, without regard to their functional status per AHA/ACC guidelines ⁷³.

3. Stratification Schema

This study is designed to stratify the randomization on two levels: site, and co-morbidity burden (Charlson score <3 and Charlson score \geq 3). An alternative schema was considered that did not include stratification by site, but the variability of geography, demography, and local clinical approaches makes site an important co-variate that should be accounted for in the final analysis. Co-morbidity burden was chosen instead of age, because stratification by co-morbidity will allow for direct testing of the possible treatment interactions by co-morbidity level. A stratification involving all three variables (i.e. site, age, and co-morbidity) was determined to not be feasible given the sample size and number of sites involved in this study.

4. Generator Changes

Consideration was given to including patients 70 years of age or older in need of an ICD generator replacement. The ICD generator requires replacement every 5-7 years depending on use with a relatively less invasive surgical procedure compared to a new ICD implantation. The

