Early effects (QoL at 6 months), late effects (QoL at 24 months), and longitudinal effects (effect over 24 months) for the Minnesota Living with Heart Failure QoL data will also be assessed by a longitudinal repeated measures mixed effects analysis. All mixed models will be adjusted for the baseline Minnesota Living with Heart Failure score, and for the randomization design (site and co-morbidity burden). Site will be included in the model as a random effect and general health status (Charlson <3 versus ≥ 3) as a fixed effect. The outcome variable in the model will be the change in the Minnesota Living with Heart Failure Quality of Life Score at each follow-up contact relative to baseline. Model building methods will be used to first determine the best mean structure of the outcome (e.g., time as linear or categorical) and then to determine the best fitting and most parsimonious covariance structure for the data.

b) All-cause Hospitalization

Total hospitalizations, total number of days of hospitalization, and the proportion of participants who require at least one hospitalization during the follow-up period will be compared between treatment groups at a 0.05 significance level. No adjustment will be made for multiple testing for tertiary outcomes because they are considered exploratory in nature. The total hospitalizations and total days of hospitalization will be analyzed using generalized Poisson or negative binomial regression models. Proportion of participants requiring at least one hospitalization will be analyzed using a chi-square test statistic.

c) Sudden Cardiac Death

Time to event for sudden cardiac death will be analyzed using the same methodology described for the primary outcome at a 0.05 2-sided significance level. VA Vital Status File will be used to determine the vital status of all study participants who are lost to follow-up at study exit. VA Vital Status File search plus a NDI Plus database search for all participants who are found to have died through the VA database search in order to adjudicate the cause of death.

5. Analysis of Safety Data

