The total number of SAE will be summarized by treatment. The proportion of participants experiencing an SAE will be calculated for each treatment group. A chi-square test for the difference in the proportion of SAEs will be used to compare treatment groups over all at the 0.05 level, and with subgroupings of SAEs and non-serious AEs at the 0.01 significance level. Treatment comparisons will be made for the number of participants experiencing SAE, the number of treatment-related SAE, and for the number of non-serious adverse events.

6. Exploratory Analyses

Additionally, data from the Informed Consent Questionnaire will be used for exploratory analysis of the association between perceived and actual participant understanding of the study. ICDs are capable of delivering information related to a wide range of parameters including activity level, heart rate variability and battery and lead status. Descriptive analysis will be used to summarize the ICD device data. The analysis will be limited in scope to three activities:

- Routine assessment of device activations to assess shock events;
- Device interrogation upon death; and

- Analysis of device data at follow-up appointments as is done in standard clinical practice.

These activities contribute substantially to optimal medical therapy.

7. Consenting Rates

Whereas there are no known published data on the willingness of elderly patients to consent into a study of this nature, it is incumbent on CSP#592 to measure and report the rates of consent among patients deemed so eligible. Data collected from patients found eligible for entry into the study will be analyzed for rate of consenting into the study, as well as rationale for non-matriculation. This activity contributes substantially to the knowledge base for the design of future clinical trials both in the study of the elderly, and in device-based trials.

XVI. FEASIBILITY

A. Estimating the Patient Population

1. ICD Candidacy among VA Patients

a) Candidacy Criteria

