2.2 Statistical and Analytical Plans

2.2.1 Randomization Scheme

Veterans who satisfy all of the study eligibility criteria, provide written informed consent and complete the necessary baseline assessments will be randomized to one of two treatment strategies: ICD therapy + optimal medical therapy, or optimal medical therapy alone. The treatment assignment will be provided through a web-based randomization platform or over the telephone to the site investigator or coordinator. The treatment allocation ratio for the two treatment regimens will be 1:1 within each stratum; participants will be stratified both by medical center and by Charlson score (Charlson <3, and Charlson \geq 3), using a random permuted block scheme with randomly varying block size. The random treatment scheme has been generated by CSPCC. When a subject is to be randomized, the Study Coordinator or Local Site Investigator will complete the eligibility and baseline forms. If all eligibility criteria are satisfied and informed consent has been obtained, a new randomization will be assigned. This procedure has been tested and validated before enrollment began.

The CSPCC will review the overall and by-site randomization at least weekly during the enrollment phase of the study, and will be monitoring the randomization transactions with equal or greater frequency. The participant's unique study ID number will be linked in the randomization file to the treatment assignment for each individual. The randomization file data will remain separate from the rest of the study data on the central database.

Randomization may occur on the same day the patient has completed the necessary portions of the Screening and Baseline assessments and is judged eligible for

randomization. Delay in randomization due to participant or medical circumstances are permitted up to a maximum of 30 days past baseline data collection; if randomization is delayed further, baseline data must be collected anew. When a new participant has been enrolled, his/her electronic medical record will be updated indicating participation in the study. Source documentation for eligibility criteria and randomization will be kept at the site with the participant's study folder.

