2.2.7.2 All-cause Hospitalization

Total hospitalizations, total number of days of hospitalization, and the proportion of participants who require at least one hospitalization during the follow-up period will be summarized by treatment and compared between treatment groups at a 0.05 significance level. No adjustment will be made for multiple testing for tertiary outcomes because they are considered exploratory in nature.

The total hospitalizations and total days of hospitalization will be analyzed using generalized Poisson or negative binomial regression models. If extra zero counts are observed in the above, a zero inflated Poisson model will be used³⁴. In the generalized mixed model, covariates will include site as a random effect, and general health status (Charlson <3 versus ≥ 3 , or as continuous variable) as a fixed effect. Proportion of participants requiring at least one hospitalization will be analyzed using a chi-square test statistic.

Considering informative censoring due to death if there is a treatment effect, we will also summarize hospitalization rate and days of hospitalization based on total active follow-up time. Similar tests as described above will be processed.

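### The final tests of the SAE and ever-hospitalised proportions ignore the randomisation strata: they stay valid, but are mildly conservative if site and Charlson predict the outcome

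*Combined protocol and SAP*

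**What the plan says.** On the design, SAP 2.2.1 (as protocol IX.A) states that "participants will be stratified both by medical center and by Charlson score", with 1:1 allocation in permuted blocks of varying size. Protocol III.G.3, explaining that choice, says that variation between centres "makes site an important co-variate that should be accounted for in the final analysis".

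On the two binary comparisons:
- **SAEs** (SAP 2.2.9; protocol XV.C.5): "A chi-square test for the difference in the proportion of SAEs will be used to compare treatment groups over all at the 0.05 level". The protocol continues "and with subgroupings of SAEs and non-serious AEs at the 0.01 significance level"; the SAP drops that clause.
- **Ever hospitalised** (SAP 2.2.7.2; protocol XV.C.4.b): "Proportion of participants requiring at least one hospitalization will be analyzed using a chi-square test statistic". Both documents class this as exploratory: "No adjustment will be made for multiple testing for tertiary outcomes because they are considered exploratory in nature".

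Other analyses do use the strata. For the number of hospitalisations and of hospital days, SAP 2.2.7.2 says that "covariates will include site as a random effect, and general health status" enters as a fixed effect. The primary log-rank test is stratified on site and Charlson in protocol XV.C.2, and on Charlson alone in SAP 2.2.3.

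**The concern.** Stratified randomisation balances the arms within each stratum, so differences between strata no longer add to the sampling error of the treatment comparison. A plain chi-square still counts that variation in its standard error. If site or Charlson predicts the outcome, the standard error is somewhat too large and so is the p-value. In a safety comparison a conservative test is not the cautious choice, because a true excess in one arm becomes slightly harder to declare.

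The documents make some prognostic strength plausible without measuring it. Protocol V.E links high Charlson scores to raised mortality. Protocol XIV.B.4 counts death and inpatient hospitalisation as SAE criteria. Protocol XII.F leaves SAE surveillance to the sites, so capture may vary by site.

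**Working it through.** **Stated figures.** The plan gives no SAE rate, hospitalisation rate or power for either test, so there is no figure on this point to reproduce. The nearest is the primary sample size, which sets N. With the SAP 2.1 assumptions (15% a year, HR 0.75, 2.5% annual drop-in, 1% year-1 drop-out, 2 to 5 years of follow-up), a Markov log-rank calculation gives 562 to 563 events. It gives N = 1,431 without loss or 1,455 with 1% annual loss, against the stated 565 and 1,462.

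**Inputs.** N = 1,462, 1:1; 27 sites × 2 Charlson levels = 54 strata, on average 1,462/54 ≈ 27 participants each. The share with Charlson <3 is (316 + 511)/4,070 ≈ 20% in protocol Table 7 (patients without an ICD), or 50% as assumed in protocol XV.A.3. *Assumed, with a range:* the outcome proportion p and the share R² of outcome variance lying between strata.

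**Formula.** The chi-square uses variance (4/N)·p(1−p). After stratified randomisation the variance is about (4/N)·p(1−p)(1−R²). Hence:
- true size = 2Φ(−1.96/√(1−R²));
- with δ = 1.960 + 0.842 (nominal power 80%), chi-square power = Φ((δ − 1.960)/√(1−R²));
- stratified-test power = Φ(δ/√(1−R²) − 1.960).

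| R² | True size | Chi-square power | Stratified power | Gap (points) |
|---|---|---|---|---|
| 0 | 5.0% | 80.0% | 80.0% | 0 |
| 2% | 4.8% | 80.2% | 80.8% | 0.6 |
| 5% | 4.4% | 80.6% | 82.0% | 1.4 |
| 10% | 3.9% | 81.3% | 84.0% | 2.7 |

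As an illustration at p = 30% (assumed): the chi-square standard error is √(4 × 0.21/1,462) = 0.0240, a 95% half-width of 4.70 points. At R² = 5% the stratified half-width is 4.70 × √0.95 = 4.58 points.

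**What R² might be.** For p from 10% to 90% and either Charlson share:
- Charlson odds ratio 1.5, between-site log-odds SD 0.2: R² 0.6–2.0%;
- odds ratio 2, SD 0.3: R² 1.3–4.9%;
- odds ratio 3, SD 0.5: R² 3.4–11.4%.

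**Simulation** (1,462 participants, 54 strata, random blocks of 2, 4 and 6, p of 30% and 70%). The power gap was 0.1 to 1.0 points for the first two settings and 1.8 to 3.0 for the third. In the third, chi-square size was 3.6–4.3% and Cochran-Mantel-Haenszel (CMH) size 4.7–5.5%. In the weaker settings chi-square size scattered between 4.4% and 5.9%, too noisy to show a shift of half a point. A separate simulation gave 79.6% v 80.7% for moderate strata and 73.8% v 77.1% for strong ones. A gap of 4 points (72% v 76%) appeared only at the extreme of the assumptions tried, with a site SD of 0.7.

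**The case against.** A reader might infer that these p-values are too large as a matter of course and that harm will be missed. The documents do not support that.

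- **The effect is conditional.** It vanishes at R² = 0, and no stratum effect on SAEs or hospitalisation is given. This stands.
- **The test is valid.** Type I error does not exceed 5%. When nominal power is above 50%, the chi-square has at least the power expected under simple randomisation, so only a possible gain is given up. This stands, with one limit: at 30% nominal power and R² = 10%, the same formulas give 29% for the chi-square against 33% stratified.
- **No decision hangs on it.** Protocol XV.B.5 and SAP 2.3.3 leave SAE proportions to the DMC's judgement, without a p-value rule. Protocol XV.A.3 and SAP 2.1 treat endpoints other than the primary as exploratory, and the hospitalisation counts and days are already adjusted. This stands.
- **Protocol III.G.3 is stretched.** It justifies stratified randomisation and does not require every safety test to use site. The SAP's own primary test omits site. This stands in part: III.G.3 gives a reason for adjustment, not a rule that has been broken.
- **CMH has a cost.** Strata in which everyone or no one has an event add nothing to the test. In simulation with 85–92% having an SAE and weak to moderate strata, CMH minus chi-square power was −0.5 to +1.1 points, with 7–23% of strata uninformative. At pilot size (102 participants, 6 sites, so 102/12 ≈ 8.5 per stratum) it was −1.6 to +0.1. A second set of runs gave 82.0% v 82.7% at a high event rate and 71.6% v 71.8% at pilot size, in favour of CMH. So the change is not free of cost in sparse data, but the gain at full size survives.

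**Conclusion.** The point holds as a modest efficiency improvement to the final analysis. Both binary comparisons ignore strata that the design created and that the neighbouring count models use, and no reason is given. If the strata explain 2% to 10% of the outcome variance, the nominal 5% test runs at about 4.8% to 3.9%, and about 0.5 to 3 points of power are forgone at 80% nominal power. These figures rest on assumed R² and outcome rates, on full enrolment of 1,462, and on strata that are prognostic; without the last, the effect is nil.

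It does not follow that the safety analysis is invalid or that DMC oversight is weakened. Stratifying also does nothing about unequal survival or follow-up between arms, which may matter more for an ever-event proportion. SAP 2.2.7.2 covers that for hospitalisation rates and days only.

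**What to change.** In SAP 2.2.9 and 2.2.7.2, and in protocol XV.C.5 and XV.C.4.b:

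1. Replace the chi-square with a Cochran-Mantel-Haenszel test stratified by Charlson (<3 v ≥3) and site.
2. Report the Mantel-Haenszel risk difference with a 95% CI, naming a variance estimator that holds with many small strata. SAP 2.2.9 currently specifies no effect estimate for SAEs.
3. State in advance what happens if site strata are too sparse, for example at pilot size: stratify by Charlson only, or pool small sites by a fixed rule.
4. In the same edit, reconcile the protocol's 0.01 level for SAE subgroupings and non-serious AEs with its absence from SAP 2.2.9.

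The cost is a few sentences and a few lines of code, with no new data. The small downside is the information lost from strata with no events or all events. The wording should be settled before any unblinded analysis, so that the choice of test cannot appear to follow the results.

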2.2.10 Consenting Rates

Whereas there are no known published data on the willingness of elderly patients to consent into a study of this nature, it is incumbent on CSP#592 to measure and report the rates of consent among patients deemed so eligible. Data collected from patients found

eligible for entry into the study will be analyzed. The total number of patients meeting ICD eligibility criteria, and the total number and percent of patients meeting each exclusion criterion will be calculated. Among the eligible patients, we will summarize the percentage of those enrolled and –as applicable– reasons for non-enrollment. Both the raw percentage and exclusive percent (pick the first exclusion for each subject) will be reported (Tables 3 and 4). This activity contributes substantially to the knowledge base for the design of future clinical trials both in the study of the elderly, and in device-based trials.

2.3 Interim Monitoring and Analysis

2.3.1 Overview

Interim monitoring of both the pilot study and the full scope study will be performed by the CSPCC. The first phase of the study will be a one-year Pilot study with six participating sites. The objective of the Pilot study is to determine feasibility of recruitment for the full study phase. The interim monitoring within the Pilot study will focus on recruitment and safety. The interim monitoring within the whole study will focus on recruitment (overall and by site), baseline comparability of treatment groups, protocol adherence, completeness of data, accrual of primary endpoint events (i.e., information accrual), safety, and treatment efficacy. Recruitment and completeness of data will also be monitored for purposes of daily trial operations and quality assurance. The CSPCC monitoring provides the basis for reporting to the Data Monitoring Committee (DMC).

2.3.2 Monitoring Recruitment

The CSPCC will monitor all steps in the recruitment process to assure early recognition of inadequate performance and to identify reasons for inadequate performance at each recruitment site and for the trial overall. To assist in this process, the CSPCC will produce weekly data monitoring reports (Table 1 and 2). These reports will include number of screening forms completed, reasons for non-matriculation into study, number of informed consent documents signed, and number of randomizations overall and by medical center. The same reports will be made available to the DMC at each of its meetings. Predicted total patient accrual for the full study will be calculated using both direct extrapolation.

In CSP#592 we may test an alternative accrual assessment approach via multicenter Bayesian method³⁸, using the recruitment goal of 17 patients per site per year as prior and the data from the Pilot study. The Bayesian prediction methods will extend the direct extrapolation method by providing a credible interval for the prediction of the recruitment which considers the uncertainty and variation during the process. The purpose of this analysis is to pursue new and different techniques for projecting study enrollment rates.

2.3.3 Monitoring Safety

Trial safety will be monitored by CSPCC and the CSPCRPCC, throughout the study, both in Pilot and full study. Safety reports will be submitted to the DMC approximately every 6 months after enrollment begins, or more frequently, if requested by the DMC. For reports to the DMC closed session, serious adverse events will be summarized by treatment groups, and relatedness to the assigned interventions.

The proportion of participants experiencing an SAE in each treatment group will be calculated. If the DMC finds the proportion of SAEs unacceptably higher in one

treatment group compared to another, the DMC may consider recommending that the trial be stopped or that the protocol be modified.

2.3.4 Monitoring Outcomes

Two interim analyses of the treatment effect on the primary endpoint of all-cause mortality will be performed when approximately half and three quarters of the events are accumulated (~280 and 420, anticipated at approximately years 3 and 4). However, the DMC will have discretion to request additional or different timing of interim analyses. A Haybittle-Peto type stopping boundary ($p < 0.001$) will be used for monitoring the study for early efficacy³⁹.

A futility analysis for the primary endpoint is also planned at the time of the interim analysis. If the analysis shows that the primary endpoint crosses the internal boundary for futility, it would indicate that the observed effect size is much smaller than anticipated and that the trial has very low conditional power to detect the estimated treatment effect for the primary outcome. The proposed stopping boundary for futility is a hazard ratio of between 1.02 and 0.98 (approximate p-value of 0.80).

In addition to these futility analyses, the observed primary outcome event rate and rate of information accrual (number of events) is monitored from the initiation of the trial and compared with the expected rates. Based on these rates, an estimated time for study completion (i.e. time to reach 565 events) and the estimated number of events that will be reached by the scheduled end of the trial will be presented to the DMC. When considering the futility analyses and rate of information accrual, the DMC may also consider other internal or external evidence of futility (i.e., secondary outcomes) and has the option of recommending early termination of the trial for futility, or continuing with a

possible adjustment to sample size. As there will not be enough events for analysis of efficacy, we will not monitor outcomes in a meaningful way in the Pilot study.

